### Data:

Data gathering will be performed by [name], MD and/or a CRNA. Data collection will occur in the PACU (Post-Anesthesia Care Unit) before the PACU nurses evaluate the patient for discharge. Assessment will occur at 1 hour and 24 hour post procedure. The assessment will occur on the next day by either a medical student and/or CRNA at the patients' bed side.

Assessment of the battlefield acupuncture efficacy will be performed by testing the incidence of PONV, incidence of postoperative anxiety, and pain. Pain will be assessed via the visual analog scale (VAS) scoring system.

A study investigator will record the following:

- 1. At times 1 hour and 24 hours the following will be assessed:
- 2. Incidence of PONV
- 3. Incidence of postoperative anxiety
- 4. Pain score on an 11-point (0 to 10) Visual Analog Scale (VAS) at rest and with activity
- 5. Postoperative opioid consumption via morphine equivalents used
- 6. Patient satisfaction with analgesia score (0 to 100%)

7. Any occurrence of acupuncture site infection, acupuncture site bleeding, allergic reaction to acupuncture needles, or scar tissue formation at site of acupuncture needle.

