#### **Statistical Analysis:**

An unpaired students-t-test procedure (two-sample assuming equal variances, two-tail significance p<0.05, 95% confidence interval) was performed to examine mean differences between the two

study groups on all continuously scaled variables. A Repeated measures ANOVA will be used to measured differences between time for continuous variables at the 2 measured time points (1 hour and 24 hours). Assumptions of normality and/or homogeneity of variance will be checked and verified. Comparisons between study groups on proportional differences will be examined using a non-parametric Fisher's Exact Chi-square test, when applied to 2x2 tables. Statistical significance will be set at a p-value  $\leq 0.05$ . All continuous data will be expressed as the mean with 95% upper and lower confidence intervals or Mean  $\pm$  Standard deviation.

A binary outcome, superiority power analysis based on a rate of 33% reduction of opioid consumption in the auricular battlefield acupuncture group compared to controls (sham auricular battlefield acupuncture) concluded 72 participants (36 patients per group) would be necessary to achieve 80% power with a p<0.05.

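### The only power figure (36 per group, 80%) comes from a binary-outcome calculation, but opioids are recorded as an amount and no binary opioid endpoint is defined, so the 80% is not established for any defined opioid endpoint

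*Combined protocol and SAP*

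**What the plan says.** The plan has one power statement, in the Statistical Analysis section: "A binary outcome, superiority power analysis based on a rate of 33% reduction of opioid consumption", with the conclusion that 36 patients per group "would be necessary to achieve 80% power with a p<0.05". It gives no control-group rate, mean or SD, and does not say whether the 33% is absolute or relative.

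The Data section lists the opioid measure as "Postoperative opioid consumption via morphine equivalents used", under the heading "At times 1 hour and 24 hours the following will be assessed". Its sentence on how efficacy will be judged refers to "testing the incidence of PONV, incidence of postoperative anxiety, and pain" and does not mention opioids. Neither section defines a yes/no opioid outcome, a cut-off or a responder rule.

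The Statistical Analysis section gives an unpaired t-test ("two-sample assuming equal variances, two-tail significance p<0.05, 95% confidence interval") for mean differences between the two "study groups on all continuously scaled variables". It adds "A Repeated measures ANOVA will be used to measured differences between time for continuous variables", and assigns Fisher's exact test to proportions in 2x2 tables. No test is named for opioids specifically.

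Two other places bear on intent. The Hypothesis and Outcomes section puts lower opioid requirements first among the expected effects. The Introduction speaks of analysing rates of opioid use alongside nausea and vomiting and anxiety.

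**The concern.** A sample size for a binary outcome rests on two proportions. A sample size for a difference in means rests on the SD. Neither result carries over to the other without further inputs. Here the power statement is labelled binary, while the only opioid variable collected is a quantity. The 80% therefore cannot be attached to the comparison that the plan appears to make.

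This matters because it is the plan's only power statement and opioid use is the only outcome it covers. A null result on mean morphine equivalents would be read as coming from an 80%-powered comparison, which the documents do not support. If a binary outcome was intended, leaving it undefined also leaves room to choose a cut-off after the data are known.

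**Working it through.** **Inputs from the documents.** 36 per group, 80% power, significance level 0.05 (two-sided as stated for the t-test; the power sentence does not restate sidedness), 33% reduction. Every control rate and every SD/mean ratio below is an assumption, because the documents give none.

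**1. Can the plan's 36 be reproduced?** Not from the stated inputs, since the control rate is missing. The usual pooled two-proportion formula is

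n = [1.960·√(2p̄(1−p̄)) + 0.842·√(p₁(1−p₁) + p₂(1−p₂))]² / (p₁−p₂)², where p̄ is the mean of p₁ and p₂.

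- Absolute 33-point drop, 0.66 v 0.33: p̄ = 0.495, n = [(1.386 + 0.562)/0.33]² = 34.8, so 35 per group.
- Relative 33% drop from 0.88 (to 0.590): 36 per group.
- Relative 33% drop from 0.50 (to 0.335): 140 per group.

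So 36 is plausible as a two-proportion answer at some rates. No arithmetic error is shown.

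**2. Binary reading under the plan's own test.** Exact two-sided Fisher power at 36 per group, by enumerating all tables:

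| Assumed rates | Type of 33% | Power |
|---|---|---|
| 0.40 v 0.07 | absolute | 90% |
| 0.50 v 0.17 | absolute | 80.2% |
| 0.66 v 0.33 | absolute | 73% |
| 0.83 v 0.50 | absolute | 80.2% |
| 0.95 v 0.62 | absolute | 93% |
| 1.00 v 0.67 | either | 99% |
| 0.905 v 0.606 | relative | 80.4% |
| 0.80 v 0.536 | relative | 58% |
| 0.70 v 0.469 | relative | 40% |

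For an absolute drop, power is below 80% only for control rates between about 0.50 and 0.83 (crossings at 0.503 and 0.827, minimum 73% near 0.66), and above 80% outside that band. For a relative drop it reaches 80% only from about 0.90 upward (crossing at 0.903).

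**3. Continuous reading.** For an equal-variance t-test with 70 degrees of freedom, the noncentral t distribution gives 80% power at a standardised difference of d = 0.67 (0.6696). If the 33% is a reduction in the mean, d = 0.33/(SD/control mean). Setting this equal to 0.6696 gives SD/mean = 0.33/0.6696 = 0.493. Power for a 33% lower mean with a common SD:

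| Assumed SD/mean | d | Power |
|---|---|---|
| 0.4 | 0.825 | 93% |
| 0.5 | 0.660 | 79% |
| 0.7 | 0.471 | 51% |
| 1.0 | 0.330 | 28% |

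A difference of 0.67 SD is a 33% reduction only when SD/mean is about 0.49. At a ratio of 0.4 it is about 27% (0.67 × 0.4).

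**4. Sensitivity to the common-SD assumption.** If the SD falls in step with the mean (lognormal data with the same SD/mean in both arms, 100,000 simulated trials), t-test power is about 92%, 80% and 41% at ratios of 0.5, 0.6 and 1.0. The threshold moves from about 0.49 to about 0.6, and the dependence on an unstated input remains.

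**The case against.** The best case for the plan is that a binary opioid outcome was intended. The Introduction refers to rates of opioid use, the power sentence itself speaks of a rate, a yes/no variable could be derived from the recorded amounts, and Fisher's test is already planned for proportions. Under that reading 36 per group can be right: it is the smallest size giving 80% Fisher power at 0.50 v 0.17 (79.5% with 35, 80.2% with 36). This makes a binary intention credible. It does not supply the variable, cut-off, time window or rates, so the 80% still cannot be checked.

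It is also fair to object that no test is tied to opioids, so the t-test is an inference from the wording on continuous variables. That stands, and the point is put as an inference. The repeated measures ANOVA, the other analysis named for continuous variables, is not a binary analysis either.

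A reader might infer that the trial is underpowered, or that 36 is a miscalculation. The documents support neither. Without a mean, SD or control rate, power may lie above or below 80% under either reading, and 36 agrees with a standard calculation at some rates.

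**Conclusion.** The point holds as a mismatch with missing inputs. The plan's single power figure belongs to a kind of outcome that the plan does not define, and the opioid outcome that it does define has no power basis. Depending on inputs the plan leaves out, 36 per group gives from 28% to 93% power for a 33% lower mean (common SD, assumed SD/mean 1.0 down to 0.4). As a binary comparison it gives 73% to 99% for an absolute 33-point drop, and 40% or 58% for a relative drop from 0.70 or 0.80.

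The mismatch itself rests only on the text. The sizes rest on assumed rates and SDs, two-sided testing at 0.05 and complete data on 36 per group. Because this is the only sample-size justification, it should be corrected before results are read against it.

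**What to change.** Rewrite the power paragraph by one of two routes, with enrolment unchanged.

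**A. If morphine equivalents are the powered outcome:** remove the description of the outcome as binary, name the t-test for this outcome and the time window it covers, and write:

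> 36 per group gives 80% power (two-sided alpha 0.05, equal-variance t-test) to detect a 0.67 SD difference in morphine equivalents; power for a 33% reduction in the mean is at least 80% if the common SD is no more than about 49% of the control mean, and lower otherwise.

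Add the assumed mean and SD with their source, or a range of power if there is no source.

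**B. If a binary opioid endpoint was intended:** define it and its time window before outcome data are seen by group, state both assumed rates and whether 33% is absolute or relative, and report Fisher power at 36 per group.

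The cost is one paragraph. The stated power may become less favourable: under A it is below 80% if the common SD exceeds about half the control mean. Route B also needs an endpoint definition and discards information on the amount of opioid used.

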#### Human Subjects (Risks & Benefits)

There may be a risk of disclosure of sensitive information. Any information containing protected health information (PHI) such as master list documents containing patient names and medical record numbers will be stored securely in a locked office inside a locked filing cabinet at the VA site. All other data will use a subject number assigned and remove all 18 types of PHI information De-identified and be hard copies (paper records) will also be stored securely in a locked office inside a locked filing cabinet. Digital data will be stored on VA servers behind the VA firewall (H: Drive [name]\$ (\\Vhadetfpc8.v11.med.va.gov) and secured in the investigator's lab (C4683 John Dingell VA Medical Center). Study data will only be accessible to investigators involved in the study. Statistical analysis will be performed on de-identified encrypted digital data at a non-VA site (Department of Anesthesiology, DMC). No financial incentives will be offered and no penalty will be applied for not participating in this study.

#### **Risks and Side Effects-Acupuncture**

The auricular battlefield acupuncture technique is considered to be safe and simple to perform. The site of needle insertion is unlikely to pose harm to any vital structures and visual identification of the auricular structures is not difficult. There are potential risks of acupuncture site infection, acupuncture site bleeding, ineffectiveness of acupuncture, worsening of localized pain symptoms following acupuncture (although unlikely), allergic reaction to acupuncture needles, and scar tissue formation at site of acupuncture needle.

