# **HYPOTHESIS AND OUTCOMES:**

The study hypothesis is that perioperative battlefield acupuncture for general surgery and urology cases undergoing general anesthesia will decrease opioid requirements, postoperative pain, the incidence of PONV, and the incidence of perioperative anxiety in comparison to simulated (placebo) perioperative battlefield acupuncture.

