#### **Acupuncture Plan**

Typically acupuncture needles which are semi-permanent needles have the characteristics of remaining in the ear acupoints for up to 3-4 days before being pushed out toward to the surface by the previous flattened epidermis. The test arm (treatment group) will received actual acupuncture needles, while the control arm will received sham or placebo acupuncture via pressing of a blunt needle on the specified BFA locations and then application of adhesive stickers. In the control group simulating acupuncture, the needles will never enter the patients' skin and will give the impression to the patient that the procedure has taken place. The ear

treated will be covered with a bandage via non-skin sensitive tape so as to blind the patient to which treatment group they are in.

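### Worsening of localized pain is a named risk of the acupuncture, but no listed item records it as an event, and the pain score does not say which site it covers

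*Combined protocol and SAP*

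**What the plan says.** The section on risks and side effects of acupuncture gives six risks. It opens with "There are potential risks of acupuncture site infection, acupuncture site bleeding, ineffectiveness of acupuncture", goes on to "worsening of localized pain symptoms following acupuncture (although unlikely", and closes with allergic reaction to the needles and scarring at the needle site.

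The Data section lists what an investigator records at 1 hour and 24 hours. Item 7 is the safety item: "Any occurrence of acupuncture site infection, acupuncture site bleeding, allergic reaction to acupuncture needles, or scar tissue formation at site of acupuncture needle". Item 4 is the only pain item: "Pain score on an 11-point (0 to 10) Visual Analog Scale (VAS) at rest and with activity". The same section makes pain an efficacy measure: "Assessment of the battlefield acupuncture efficacy will be performed by testing the incidence of PONV, incidence of postoperative anxiety, and pain". The hypothesis speaks of postoperative pain in general and gives no site.

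The Anesthetic Plan has the real or sham procedure performed in the PACU. Under the Acupuncture Plan, real needles may stay in the ear for up to 3-4 days. For the sham, a blunt needle is pressed on the same points and "the needles will never enter the patients' skin".

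**The concern.** Item 7 follows the risk section closely for four physical harms and omits the fifth. It has no entry for other events, and no other item in the text available for review records local pain as an event. An investigator who follows the list as written ends the trial with no count for a risk that the protocol itself names.

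The only other place for such pain is the item 4 score, which is not tied to a site. A patient with a sore ear and a sore wound gives one number at rest and one with activity, and nothing says whether the ear belongs in them. If it is left out, the harm is lost. If it is included, a harm sits inside an efficacy measure. Because the arms differ in what is done to the ear, the mixing could also differ between them.

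**Working it through.** The plan gives no figure on this point, so the check sets its two lists side by side.

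**Step 1: risks named against events recorded.**

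| Risk named | Recorded in item 7 | Covered elsewhere |
|---|---|---|
| Site infection | Yes | – |
| Site bleeding | Yes | – |
| Ineffectiveness | No | Yes: lack of benefit, shown by the efficacy outcomes |
| Worsening of localized pain | No | Not as an event; at most part of the item 4 score |
| Allergic reaction | Yes | – |
| Scarring | Yes | – |

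Without ineffectiveness, which is not a physical harm, five physical harms remain. Four are recorded and one is not (1/5 = 20%).

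**Step 2: the two readings of the phrase.**

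- *Pain at the ear.* No item asks about it. Item 4 may or may not include it, and a single number cannot be split afterwards.
- *Worsening of the pain being treated.* Items 4 and 5 (pain score and opioid use) would reflect this in part, as a difference between arms. But worsening in a given patient needs a value from before needling, and the listed assessments are at 1 and 24 hours only. A change from 1 to 24 hours starts after treatment, and a difference in means is not a count of patients harmed.

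Under either reading the risk is not counted.

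**Step 3: direction of any mixing.** Let q be the share of an arm with ear pain and d the points it adds to the score. The shift in the difference between arm means is

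q(treatment) × d(treatment) − q(sham) × d(sham).

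Puncture pain can arise only in the treatment arm, and the needles may still be in place at both assessments. The first term may therefore be the larger, which would make acupuncture look worse. Blunt pressing may also leave the ear tender, so the second term is not known to be zero. If the two terms are equal, the shift is zero.

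**Step 4: illustration only.** The documents give neither q nor d. Assume q(treatment) of 5%, 10% or 20%, d of 1 to 3 points fully added to the score, and no ear pain under sham:

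- 5%: 0.05 × 1 to 0.05 × 3 = 0.05 to 0.15 points
- 10%: 0.10 to 0.30 points
- 20%: 0.20 to 0.60 points

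These values depend wholly on the assumptions and estimate nothing about this trial.

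At the same assumed rates, the chance that at least one of the 36 treated patients (Statistical Analysis section) has ear pain is 1 − (1 − q)^36:

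- 5%: 1 − 0.95^36 = 84%
- 10%: 1 − 0.90^36 = 98%
- 20%: 1 − 0.80^36 = over 99.9%

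So even at the lowest of these rates there would probably be something to record.

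**The case against.** The phrase need not mean the ear. Infection, bleeding and scarring are each tied to the acupuncture or needle site; the pain risk is not. Worsening presupposes pain already present, and the phrase comes straight after ineffectiveness. On that reading, leaving it to the efficacy outcomes is coherent. This stands as a reason not to assert the ear reading. It does not close the gap, because without a score before needling no patient can be classed as worse.

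The context of item 4 also points to the wound: the hypothesis concerns postoperative pain, the rest and activity split suits surgical pain, and item 6 asks about satisfaction with analgesia. This makes the intended site inferable, but the item does not state it.

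Parts of the document were not available to read, and no data form is included. A general adverse-event provision elsewhere cannot be ruled out. This lowers confidence.

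A reader might go further and infer that any ear pain raises the score in the acupuncture arm only, shifting the comparison by several tenths of a point. The documents do not support that. Patients would have to include the ear and add it to their wound pain, and the sham would have to cause no tenderness; neither is shown. No rate is given either, and the only indication of frequency is that the risk is thought unlikely.

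**Conclusion.** The recording gap holds: one of the five physical harms that the protocol names has no item that counts it, whichever way the phrase is read. It also holds that item 4 leaves its site unstated, so ear pain could be lost or could enter the efficacy score. Any mixing may be larger in the treatment arm and would then count against acupuncture, so it could hide a benefit rather than create one. Its size cannot be computed from the documents.

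The conclusion rests on the Data list being what is actually collected and on there being no general adverse-event item in the parts that could not be read. Severity is minor; confidence is moderate.

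**What to change.** In the Data section:

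- Add to item 7: new or worse pain at the treated ear (yes/no, and 0-10 if yes). Ask it with identical wording in both arms at 1 and 24 hours, after item 4.
- Reword item 4 to ask for pain at the surgical site, keeping the rest and activity scores.

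In the risk section, say which pain is meant. If it is the treated pain, the reworded item 4 gives a comparison between arms, but a count of patients who worsened would still need a score from before needling.

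The cost is one question and a few words at assessments already planned. The treatment arm's harm rate may look less favourable. There is also a small risk to blinding: asking about the ear at 1 hour may draw attention to allocation before the 24-hour ratings, and asking item 4 first does not remove that carry-over. Item 7 already asks about the needle site in both arms, so the added risk should be slight.

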#### **Benefits:**

A direct benefit to patients may be a decrease in post-operative opioid requirements, decreased postoperative pain decreased incidence of PONV and decreased perioperative anxiety.

The societal benefits to participating in this study may be improved knowledge of anesthesia practice methods in improving post-operative pain control and reducing side effects for patients in the future. There is no financial benefit to participating in this study.

#### **Retention of Records/Ethical Issues**

Each patient will be assigned a unique three-digit number that will be linked to a separate list located in the regulatory binder. None of the sensitive material including but not limited to the patient's name, identification number, date of birth, etc., will be accessible to any individual except to those involved in the study. Removal of access to research study data will occur for study personnel when they are no longer part of the research team. All patient data will be kept in a locked cabinet in a locked room in the P.I's secure office. All VA research data will be stored and disposed of according to the current VA Record Retention Policy. In accordance with VA policy, procedures will be put in place for reporting incidents, i.e. theft or loss of data or storage media, unauthorized access of sensitive data or storage devices or non-compliance with security controls. None of the investigators, co-investigators, or other key personnel will receive any financial benefits from the research study. The study will be conducted at the John Dingell Veteran Affairs Medical Center (VA) by the Department of Anesthesiology at Wayne State University, pending approval by the CIC VA and the Human Investigation Committee at Wayne State University.

#### **IRB Review**

#### Battlefield Acupuncture Protocol with Statistical Analysis Plan 06/09/2018

Investigators will prepare and submit all required documentation and obtain John D. Dingell VA Medical Center Internal Review Board (IRB) approval to implement the study prior to conducting the research. Notification to the John D. Dingell VA Medical Center IRB office regarding any changes to the protocol will be filed as amendments and not initiated until approval is obtained. Final closure of the study will be filed with the John D. Dingell VA Medical Center IRB office. All investigators have completed the mandatory Human Research Participant On-line Training (CITI Program).

#### **Outside Consultants/Collaborators**

Non

# Contractual Agreements

N/A

#### Costs To Subjects:

There will be no additional costs to subjects as a result of taking part in this study. The anesthetic care of the patient, including the medications that are used as part of the patient's management and recovery, are subject to billing by the medical personnel at John D. Dingell VA Medical Center.

